7.1 Discontinuation of study treatment

Subjects may voluntarily discontinue study treatment for any reason at any time.

The investigator must discontinue study treatment for a given subject if, on balance, he/she believes that continuation would be detrimental to the subject's well-being.

Study treatment must be discontinued under the following circumstances:

- Subject withdraws consent
- Pregnancy

- The subject experiences a drug-related serious adverse event
- Absolute QTcF (or QTcB) >500 msec, as confirmed by repeat ECG measurements performed as soon as possible
- Diarrhea of CTCAE grade ≥ 2 on more than 3 consecutive days
- Diarrhea of CTCAE Grade 3 or higher
- Diarrhea or abdominal pain with accompanying fever assessed to be related to a gastrointestinal infection
- Increase of methotrexate dose and/or corticosteroid dose and/or chloroquine during 12 weeks of dosing (see [Section 6.10](#)).

The patient will be discontinued from study treatment and will continue in the study if deviating from the prescribed dose regimen for study treatment:

- More than 28 missed doses of study treatment cumulatively (i.e., 14 days, whether consecutive or not)

Discontinuation of study treatment will be at the discretion of the Investigator, under the following circumstances:

- Any protocol deviation or adverse event that results in a significant risk to the patient's safety
- Use of prohibited treatment other than described under Concomitant Treatment, please see also [Section 5.2](#)

The appropriate personnel from the site and Novartis will assess whether study treatment should be discontinued for any subject whose treatment code has been broken inadvertently for any reason.

Subjects who discontinue study treatment should NOT be considered withdrawn from the study UNLESS they withdraw their consent. They should return for all assessments as presented in the [Assessment schedule](#). If they fail to return for these assessments for unknown reasons, every effort (e.g. telephone, email and letter) should be made to contact them.

7.2 Study completion and post-study treatment

Each subject will be required to complete the study in its entirety and thereafter no further study treatment will be made available to them. Study completion is defined as when the last subject completes their End of Study visit, and any repeat assessments associated with this visit have been documented and followed-up appropriately by the Investigator, or in the event of an early study termination decision, the date of that decision.

The investigator must provide follow-up medical care for all subjects who are prematurely withdrawn from the study, or must refer them for appropriate ongoing care.

7.3 Lost to follow-up

For subjects whose status is unclear because they fail to appear for study visits without stating an intention to discontinue or withdraw, the investigator should show "due diligence" by documenting in the source documents steps taken to contact the subject, e.g. dates of telephone calls, registered letters, etc. A subject should not be formally considered lost to follow-up until his/her scheduled end of study visit would have occurred.

7.4 Withdrawal of informed consent

Subjects may voluntarily withdraw consent to participate in the study for any reason at any time.

Withdrawal of consent occurs only when a subject does not want to participate in the study anymore **and/or** does not want any further visits or assessments **and/or** does not want any further study related contact **and/or** does not allow analysis of already obtained biologic material.

If a subject withdraws consent, the investigator must make every effort to determine the primary reason for this decision and record this information. Study treatment must be discontinued and no further assessments conducted. All biological material that has not been analyzed at the time of withdrawal must not be used. Further attempts to contact the subject are not allowed unless safety findings require communicating or follow-up.

7.5 Replacement of early withdraws or discontinuations

The sponsor may replace patients who withdrew or discontinued from study treatment before study week 13.

7.6 Study Stopping rules

The **study** will be put on temporary hold and safety data will be reviewed if any of the following criteria are met, and no further enrollment will take place pending a full safety review conducted by the sponsor:

- Two or more subjects experience a drug-related serious adverse event
- Three or more subjects report CTCAE (current version) Grade 3 or higher adverse events within the same organ class that are considered to be related to study drug
- The sponsor considers that the number and/or severity of adverse events justify discontinuation of the study
- The sponsor requests it

7.7 Early study termination by the sponsor

The study can be terminated by Novartis at any time for any reason. This may include reasons related to the benefit/ risk assessment of participating in the study, practical reasons (including slow enrollment), or for regulatory or medical reasons. Should this be necessary, subjects must be seen as soon as possible and treated as a prematurely withdrawn subject. The investigator may be informed of additional procedures to be followed in order to ensure that adequate consideration is given to the protection of the subject's interests. The investigator will be responsible for informing IRBs/IECs of the early termination of the trial.

8 Procedures and assessments

Table 8-1 Assessment schedule

Subjects should be seen for all visits on the designated day, with the assessments performed as per schedule, within the allowed “visit/assessment window” specified in below table.

| Study Period | Screening | Baseline | Treatment Period (Placebo- Controlled) | | | | | | End of Study |
|---|---------------|----------------------|--|----------|---------|----------------------|----------------------|----------------------|--------------|
| Visit Numbers/ NCDS | V1/ V1 | V2/ V2 | V3/ V101 | V4/ V102 | V5/V103 | V6/ V104 | V7/ V105 | V8/ V106 | V199 |
| Week | Wk -4 to -1 | Week -1 | Week 1 | Week 2 | Week 3 | Week 5 | Week 9 | Week 13 | Week17 |
| Day | Day -28 to -2 | Day -1 | Day 1 | Day 8 | Day 15 | Day 29 | Day 57 | Day 85 ⁹ | Day 113 |
| Visit window (day) | | | | +/- 1d | +/- 2d | +/- 2d | +/- 3d | +/-3d | +/- 4d |
| Obtain informed consent | X | | | | | | | | |
| Inclusion / Exclusion criteria | X | X | | | | | | | |
| Relevant medical history and current medical conditions | X | X | | | | | | | |
| Demography (including smoking status) | X | | | | | | | | |
| Physical examination ¹¹ | X | X | | X | X | X | X | X | X |
| Hepatitis and HIV screen ¹⁰ | X | | | | | | | | |
| Pregnancy test | X | Predose ³ | | | | Predose ² | Predose ² | Predose ² | X |
| Tuberculosis Quantiferon test ¹⁰ | X | | | | | | | | |
| Alcohol and drug screen ¹⁰ | X | | | | | | | | |
| Perform IRT call | X | X | | | | | | | |
| Randomization (via IRT) | | X | | | | | | | |
| Vital signs and body measurements | | | | | | | | | |
| Body height | X | | | | | | | | |
| Body weight | X | X ³ | | | | X | X | X | X |
| Body temperature | X | Predose ³ | | Predose | Predose | Predose | Predose | Predose | X |

| Study Period | Screening | Baseline | Treatment Period (Placebo- Controlled) | | | | | | End of Study |
|---|---------------|----------------------|--|------------------|---------|----------|----------|----------------------|------------------|
| Visit Numbers/ NCDS | V1/ V1 | V2/ V2 | V3/ V101 | V4/ V102 | V5/V103 | V6/ V104 | V7/ V105 | V8/ V106 | V199 |
| Week | Wk -4 to -1 | Week -1 | Week 1 | Week 2 | Week 3 | Week 5 | Week 9 | Week 13 | Week17 |
| Day | Day -28 to -2 | Day -1 | Day 1 | Day 8 | Day 15 | Day 29 | Day 57 | Day 85 ⁹ | Day 113 |
| Visit window (day) | | | | +/- 1d | +/- 2d | +/- 2d | +/- 3d | +/-3d | +/- 4d |
| Blood pressure / Pulse rate | X | | Predose 1,3,5 h | Predose 1,3 h | Predose | Predose | Predose | Predose | X |
| ECG evaluation (triplicate) | X | | Predose 1,3,5 h | Predose 1,3 h | Predose | Predose | Predose | Predose | X |
| Hematology, Blood chemistry, Urinalysis | X | Predose ³ | | Predose | Predose | Predose | Predose | Predose | X |
| hsCRP | X | Predose ³ | | Predose | Predose | Predose | Predose | Predose | X |
| Corporate Confidential Information | X | Predose ³ | | Predose | Predose | Predose | Predose | Predose | X |
| Corporate Confidential Information | X | Predose ³ | | Predose | Predose | Predose | Predose | Predose | X ⁵ |
| Corporate Confidential Information | X | Predose ³ | | | | Predose | Predose | Predose | X |
| ESSDAI | X | X ⁴ | | | | X | X | X | X |
| ESSPRI | X | X ⁴ | | | | X | X | X | X |
| Patient Questionnaires, MFI, SF-36 | X | X ⁴ | | | | X | X | X | X |
| Visual Assessment Scale (VAS) (Investigator & Patient) | | X ⁴ | | | | X | X | X | X |
| Corporate Confidential Information | | Predose ³ | | | | | | Predose | X |
| Corporate Confidential Information | X | Predose ³ | | | | | | Predose | X |
| Corporate Confidential Information | | X ¹ | Predose ¹ | | | | | Predose ¹ | X ^{5,1} |
| PK blood collection | | | Predose 0.5,1,3,5,7h | Predose 1,3 h | Predose | Predose | Predose | Predose | |
| Corporate Confidential Information | | X ¹² | Predose 1,3,5 h | Predose 1,3 h | Predose | Predose | Predose | Predose | X ⁵ |
| Corporate Confidential Information | | X | Predose | Predose | Predose | Predose | Predose | Predose | X ⁵ |
| Corporate Confidential Information | X | Predose ³ | | Predose | Predose | Predose | Predose | Predose | X |
| Corporate Coi | | X | Predose | | | Predose | Predose | Predose | X ⁵ |

8.1 Informed consent procedures

Eligible subjects may only be included in the study after providing written (witnessed, where required by law or regulation), IRB/IEC-approved informed consent.

Informed consent must be obtained before conducting any study-specific procedures (i.e. all of the procedures described in the protocol). The process of obtaining informed consent should be documented in the subject source documents.

The date of signing of informed consent (and withdrawal, if later withdrawn) should be documented in the CRF.

Novartis will provide to investigators a proposed informed consent form that complies with the ICH GCP guideline and regulatory requirements and is considered appropriate for this study. The informed consent form will also include a section related to optional future research which will require a separate signature if the subject agrees to future research. Novartis will review the Investigators proposed informed consent form to ensure it complies with the ICHE6 GCP guideline and regulatory requirements and is considered appropriate for this study. Any changes to the proposed consent form suggested by the investigator must be agreed to by Novartis before submission to the IRB/IEC.

Pregnancy outcomes must be collected for the female partners of any males who took study treatment in this study. Consent to report information regarding these pregnancy outcomes should be obtained from the mother.

Corporate Confidential Information

In the event that Novartis wants to perform testing on the samples that are not described in this protocol, additional Institutional Review Board and/or Ethics Committee approval will be obtained.

A copy of the approved version of all consent forms must be provided to the Novartis monitor after IRB/IEC approval.

8.2 Subject screening

In general it is permissible to re-screen a patient if s/he fails the initial screening; however, each case must be discussed and agreed with the Sponsor on a case-by-case basis.

Information on what data should be collected for screening failures is outlined in the Site Operations Manual.

8.3 Subject demographics/other baseline characteristics

Subject demographic and baseline characteristic data will be collected on all subjects.

Relevant medical history/current medical conditions data includes data until signature of informed consent. Where possible, the diagnoses and not symptoms will be recorded.

Medications, over-the-counter drugs and significant non-drug therapies (including physical therapy and blood transfusions) prior to the start of the study will also be recorded.

Investigators have the discretion to record abnormal test findings on the medical history CRF whenever in their judgment, the test abnormality occurred prior to the informed consent signature.

8.3.1 Hepatitis/HIV screening

All patients will be screened for Hepatitis B surface antigen (HBsAg). Screening for Hepatitis C will be based on HCV antibodies.

Evaluation for HIV seropositivity will be performed, and, if positive, confirmation by a second technique available at the laboratory, e.g. Western Blot.

Appropriate counseling will be made available by the Investigator in the event of a positive finding. Notification of state and federal authorities, as required by local law, will be the responsibility of the Investigator.

Results will be available as source data and will not be recorded within the CRF.

8.3.2 Tuberculosis testing

In order to evaluate a possible infection or latent infection with tuberculosis, a Quantiferon Gold[®] test will be performed and read at screening.

A positive QuantiFeron test at screening will exclude the subjects from the participation in the study. Results will be available as source data and will not be recorded within the (e)CRF.

8.3.3 Alcohol test, Drug screen

Subjects will be tested for substances of abuse (e.g., alcohol, amphetamines, barbiturates, benzodiazepines, cannabinoids, cocaine, and opiates).

Results will be available as source data and will not be recorded within the (e)CRF.

8.4 Efficacy

In addition to assessments for safety, PK and PD, exploratory clinical efficacy measurements will include components of the ESSDAI and of the ESSPRI and other patient-based assessments, along with imaging, histopathology and functional assessments of the exocrine glands.

Corporate Confidential Information

8.4.1 ESSPRI

The ESSPRI ([Appendix 7](#)) is an established disease outcome measure for Sjögren's syndrome. It consists of a questionnaire developed to assess the patients' symptoms in primary Sjögren's syndrome and covers the three key subjective areas of discomfort, i.e., dryness, pain and fatigue ([Seror et al 2011](#)). The full questionnaire has 21 questions. Subsequently, it was noted that the first three questions, Likert scales ranging from 0 – 10, capture the essence of the ESSPRI. This abbreviated version was used to define the “minimal clinically important improvement” (0.67 – 1) and the “patient-acceptable symptom state” (<5) ([Seror et al 2016](#)).

Study subjects in the present study will be asked to complete the full ESSPRI questionnaire. However the mean of the first three questions is used for the primary analysis and for the assessment of eligibility.

8.4.2 ESSDAI

The ESSDAI ([Appendix 6](#)) is an established disease outcome measure for Sjögren's syndrome. The instrument contains 12 organ-specific domains contributing to disease activity. For each domain, features of disease activity are scored in 3 or 4 levels according to their severity. These scores are then summed across the 12 domains in a weighted manner to provide the total score.

For assessments not listed in the protocol as mandatory tests but which may be needed to estimate ESSDAI, including radiography, high resolution computer tomography (HRCT), lung function test (DLCO, FVC), estimated glomerular filtration rate (eGFR), electromyography (EMG), muscle (or any other) biopsy, it is at the investigator's discretion to have these assessed based on the signs and symptoms of the patient so to provide correct ESSDAI readout.

8.4.3 SF-36

The Short Form Health Survey (SF-36) is a survey evaluating individual patients' health status which also monitors and compares patients' disease burden ([Appendix 8](#)).

The SF-36 consists of eight scaled scores (vitality, physical functioning, bodily pain, general health perceptions, physical role functioning, emotional role functioning, social role functioning, mental health), which are the weighted sums of the questions in their section.

8.4.4 MFI

The Multidimensional Fatigue Inventory (MFI) is a 20-item self-report instrument designed to measure fatigue covering the following dimensions: General Fatigue, Physical Fatigue, Mental Fatigue, Reduced Motivation and Reduced Activity ([Appendix 9](#)).

8.4.5 Global assessments (VAS) of disease activity

8.4.5.1 Physician's global assessment

The physician's global assessment of disease activity will be performed using 100 mm VAS ranging from no disease activity to maximal disease activity, after the question “Considering

all the ways the disease affects your patient, draw a line on the scale for how well his or her condition is today”.

The investigator will then measure the distance in mm from the left edge of the scale and the value will be entered on the eCRF.

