8.4.5.2 Patient’s global assessment

The patient’s global assessment of disease activity will be performed using 100 mm VAS ranging from no disease activity to maximal disease activity, after the question on how well the patient is doing with the disease considering all aspects affected by the disease.

The investigator will then measure the distance in mm from the left edge of the scale and the value will be entered on the eCRF.

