8.4.6 Patient-Reported Outcome

Refer to [Section 8.4.1](#), [Section 8.4.2](#), [Section 8.4.3](#) and [Section 8.4.4](#) for patient-reported Outcome.

The patients will be asked to complete a paper copy of the questionnaires or VAS scale in their local language. The printed copy will serve as source data and the patients’ responses will be transcribed into the eCRF.

Completed questionnaires and VAS scale will be reviewed and examined by the Investigator before the clinical examination for responses which may indicate potential AEs or SAEs. The Investigator should review not only the responses to the VAS scale, but also for any unsolicited comments written by the patient.

If the occurrence of AEs or SAEs is confirmed, the Investigator should record the events as per instructions given in [Section 9](#) Investigators should not encourage the patients to change the responses reported on the VAS scale.

Corporate Confidential Information

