6.2 Secondary objectives

6.2.1 Variables

Secondary efficacy variables supporting the secondary objectives are:

- Change from baseline in ESSDAI
- Change from baseline in SF-36 for both physical and mental component
- Change from baseline in MFI
- Change from baseline in Physician and Patient VAS of global disease activity

There was a scaling problem with the printed batch for the CRF sheets for the VAS scale in Hungary. The line that is printed and which is marked by either the patient or the physician should be 100mm long, but in the Hungarian site both VAS scales only measured 95mm therefore both VAS scales for the Hungarian site will be transformed by multiplying by 1.053 to get comparable results to the German site.

In the listings both the actual measurement and the value based on a length of 100mm will be presented with the transformed results based on a length of 100mm used in all other VAS outputs.

The key timepoint is the week 13 visit.

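### The global VAS questions are worded by wellness while the line is anchored by disease activity, and the readable text has no direction check; this affects two secondary endpoints only

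*Protocol*

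**What the plan says.** **Physician VAS (Protocol 8.4.5.1).** The scale is a "100 mm VAS ranging from no disease activity to maximal disease activity". The question is given verbatim and ends by asking the physician to "draw a line on the scale for how well his or her condition is today". Scoring follows: "The investigator will then measure the distance in mm from the left edge of the scale".

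**Patient VAS (Protocol 8.4.5.2).** Anchors and scoring are the same. The question is described, not reproduced: the mark is made "after the question on how well the patient is doing with the disease considering all aspects affected by the disease".

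**Handling of completed forms (Protocol 8.4.6).** Forms are on paper and in the local language. The investigator reviews them before the clinical examination "for responses which may indicate potential AEs or SAEs". The section closes with: "Investigators should not encourage the patients to change the responses reported on the VAS scale".

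**Status and data handling.** Protocol 2.2 makes each VAS the only endpoint of its own secondary objective. SAP 6.2.1 lists "Change from baseline in Physician and Patient VAS of global disease activity" among the secondary efficacy variables, with week 13 as the key timepoint. The one VAS correction in the readable SAP concerns length: the line on the Hungarian sheets measured 95 mm, so those values are multiplied by 1.053. Direction is not mentioned.

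**The concern.** The question and the line point opposite ways. In answer to how well someone is, more means better; on a line that measures activity from the left, more means worse. A rater who answers the question literally and puts a patient who is doing well far along the line is recorded as having near-maximal disease activity.

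The error could be large for a single patient, and the arms are small. A mark on the wrong end is still a legal value between 0 and 100 mm, so a range check would not find it. The review in 8.4.6 looks for adverse events, not for direction. For the patient VAS, an investigator who suspects a reversed mark is also told not to encourage a change. At stake are the estimates for the two global assessments.

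**Working it through.** The plan states no figure on this point, so there is none to reproduce. The check is a comparison of texts followed by simple arithmetic.

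**1. Direction of question and scale**

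| | Physician VAS (8.4.5.1) | Patient VAS (8.4.5.2) |
|---|---|---|
| Question | wellness today, given verbatim | wellness, paraphrased only |
| Line | none to maximal activity | none to maximal activity |
| Score | mm from the left edge | mm from the left edge |
| Left end named explicitly | no, implied by the order of the anchors | no, implied by the order of the anchors |
| Direction check | none readable | none readable |
| Limit on prompting a change | none | yes, 8.4.6 |

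The mismatch is certain for the physician question. For the patient question it is as described, subject to the printed sheet.

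**2. One mark reversed at one visit**

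A true value *x* is recorded as 100 − *x*, an error of 100 − 2*x*. In an arm of *n* patients the mean moves by (100 − 2*x*)/*n*. The arm sizes of 16 and 8 are those analysed for ESSPRI in Protocol 11.6, borrowed here. The values of *x* are assumptions.

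| True *x* | Recorded | Error | Mean shift, n = 16 | Mean shift, n = 8 |
|---|---|---|---|---|
| 60 mm | 40 mm | −20 mm | −1.25 mm | −2.5 mm |
| 70 mm | 30 mm | −40 mm | −2.5 mm | −5 mm |
| 80 mm | 20 mm | −60 mm | −3.75 mm | −7.5 mm |

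**3. Which way the treatment difference moves**

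Take a true value of 70 mm and change = week 13 minus baseline.

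- CDZ173, week 13 reversed: change is 40 mm too low, so the drug looks better by 40/16 = 2.5 mm.
- CDZ173, baseline reversed: change is 40 mm too high, so the drug looks worse by 2.5 mm.
- Placebo, week 13 reversed: placebo looks better by 40/8 = 5 mm, so the difference shrinks.
- Placebo, baseline reversed: placebo looks worse by 5 mm, so the difference grows.

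A single reversal can therefore inflate or dilute the effect.

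**4. The same patient reversed at every visit**

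The recorded change is (100 − *x*₁₃) − (100 − *x*₀) = −(*x*₁₃ − *x*₀), so the sign flips. If a share *r* is reversed throughout, independently of treatment and of the size of the change, the expected difference is (1 − *r*)Δ − *r*Δ = (1 − 2*r*)Δ. For *r* of 5%, 10%, 20% and 30% this leaves 90%, 80%, 60% and 40% of the true difference. The documents give no reversal rate; these values show only how the result depends on *r*.

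**The case against.** The strongest reply is that the anchors are part of the scale. Each section is titled as an assessment of disease activity, and a rater marks between two described ends. Reversal requires overlooking them, and nothing in the documents suggests that it happened. This largely stands: it is why the rate is probably low and the point minor.

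General safeguards also exist. The investigator sees the patient's form and measures each mark, automated programs look for discrepancies (Protocol 10.2), and staff review eCRF entries and raise queries (Protocol 10.3). These could catch a glaring value, but none is described as looking at direction.

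Four stronger readings are tempting, and the documents do not support them:

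- **That the protocol discourages correcting either scale.** The sentence in 8.4.6 covers patients' responses only and sits in the adverse event review, where its evident aim is to stop investigators influencing patients. Nothing restricts a physician from correcting his or her own mark.
- **That both printed forms are known to ask about wellness.** Only the physician question is reproduced. The sheets and translations are not in the documents.
- **That reversals must dilute the effect.** This holds in expectation for consistent, non-differential reversal, but not for a single mark.
- **That a loss of power can be stated.** No VAS standard deviation, effect size or reversal rate is readable, Protocol 11.5.1 is redacted, and the one-sided 10% criterion is stated only for ESSPRI. Any power figure would follow from the reviewer's own assumptions.

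The 95 mm printing fault shows that an error on these sheets is possible. It is not evidence of reversed marks.

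**Conclusion.** The point holds as a minor wording defect. The physician question conflicts in direction with its own anchors, the patient question is described in the same way, and no direction-specific instruction or check is readable. Only the two secondary VAS endpoints are exposed; the ESSPRI analysis and the sample size are unaffected.

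The size cannot be estimated because the reversal rate is unknown. What can be said is that one 70 mm mark recorded as 30 mm moves an arm mean by 5 mm (n = 8) or 2.5 mm (n = 16), with the sign set by arm and visit. That rests on an assumed true value and on the ESSPRI arm sizes applying to the VAS.

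**What to change.** **If sheets are not yet in use:** in 8.4.5.1, in 8.4.5.2 and on the forms, ask how active the disease is today, from none to maximal, and state that the left edge is no disease activity. The cost is one sentence on two forms, with translation.

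**If sheets are already in use:** SAP 6.2.1 describes the printing fault in the past tense, so this is the likelier case.

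- Leave the wording unchanged, so that a patient's baseline and week 13 marks stay comparable.
- At the blinded data review already foreseen in SAP 6.1.3, list visits where one VAS is grossly discordant with the other VAS and with ESSPRI, which the assessment schedule collects at the same visits.
- Fix the threshold in the SAP beforehand. As a guide, if the two VAS would otherwise agree, a reversal opens a gap of |100 − 2*x*|, so a 40 mm cut-off would catch true values of 70 mm and above or 30 mm and below.
- Keep all marks in the main summary, and repeat it without the flagged marks only as a sensitivity analysis.

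The cost is one listing and one table. The drawback is that genuine discordance may be flagged: ESSPRI covers dryness, fatigue and pain, and physician and patient may simply disagree. That is why flagged marks stay in the main summary.
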